Various studies have been performed to evaluate the effects of occlusal reduction on the treatment of pain and discomfort (5-7). However, whether it is an effective intervention in the management of post-operative pain after root canal therapy remains controversial. Although a study by Rosenberg et al. showed that it reduced pain (5) other researchers did not find significant differences in the patients' post-procedural pain (6,7).

Cryotherapy is a treatment in which a particular body segment is exposed to cold temperatures. It aims to decrease the targeted tissue temperature to promote healing and aid in other therapeutic effects such as diminishing edema, inflammation, and pain. Cryotherapy used in dentistry has shown a role in decreasing pain after periodontal surgeries, extractions, and implant surgeries (8). In 2015, intra-canal cryotherapy was introduced in the endodontic field as a successful treatment in reducing post-endodontic pain (9). Cryotherapy in endodontics is applied in the form of applying a final cold irrigating solution into the canal.

Several studies demonstrated that there was a significant reduction in post-endodontic pain after cryotherapy (10-12). Currently, there is no study comparing the effects of

cryotherapy application and occlusal reduction. Therefore, this study will evaluate the effects of cryotherapy applications on post-operative pain on root canal-treated teeth with symptomatic apical periodontitis in comparison to occlusal reduction.

The null hypothesis assumes that there is no difference in the intensity of post-endodontic pain between the control, occlusal reduction, and cryotherapy groups in patients with symptomatic apical periodontitis. Whereas the alternative hypothesis assumes that the intensity of post-endodontic pain will be less in the cryotherapy group than in the occlusal and control group in patients with symptomatic apical periodontitis.

3. Research Question: Is there is a difference in post-endodontic pain intensity following using ccryotherapyy or occlusal reduction in patients with symptomatic apical periodontitis on mandibular first molars?

4. Rationale:

Pain can have an effect of diminishing quality of life regardless of its type and source. When pain is ongoing, it will produce anxiety and emotional distress. Therefore, pain management during treatment is an essential aspect. This study aims to establish if postoperative pain after root canal treatment can be prevented by the application of cryotherapy greater than occlusal reduction. If pain is prevented, the need for analgesics and patient's distress is reduced.

5. Objectives:

To compare the intensity of post endodontic treatment pain following final rinse using cold saline in comparison to room temperature saline and occlusal reduction.

6. Conceptual/Operational definitions:

- **Dependent factors:** Intensity of post-endodontic pain
- **Independent factors:** Occlusal Reduction, Cryotherapy (cooled saline final irrigant), and room temperature saline.
- conceptual definitions

- Post-endodontic pain: highly unpleasant sensation caused following root canal procedures.
- Occlusal reduction: a procedure in which occlusal interferences are removed using articulating paper, occlusal contacts are highlighted and grinded.
- Cryotherapy: the use of extreme cold in surgery or other medical treatment. Final cold irrigating solution is placed in a refrigerator at 2.5C and applied to the canal.

7. Materials & Methods

7.1. Research design

The research design will be a prospective randomized controlled clinical trial. The patient will be asked to pick an opaque sealed envelope that will contain a number from 1 to 3. The resultant number will determine in which group are the participants to be placed. Single blinding will be maintained in this study as patients will not be aware of their group/used irrigant.

7.2. Study population

The study population consists of 60 participants, aged 18–70 years, who will sign the informed consent. The number of participants is chosen according to a previous study (12).

Inclusion criteria

1. Age: 18–70 years
2. A patient diagnosed with symptomatic irreversible pulpitis/acute apical periodontitis
3. require endodontic therapy
4. Mandibular first molars that are diagnosed with symptomatic irreversible pulpitis/acute apical periodontitis
5. Healthy patients without systemic disease
6. Permanent mature first mandibular molars

Exclusion criteria

1. Medically compromised patients

2. Pregnant patients
3. Teeth with incomplete apex formation
4. Teeth with calcified canals
5. Periapical abscess
6. Patients on antibiotic therapy

7.3. Sample size calculation

The study will be conducted on 60 patients: with 20 first mandibular molars in each group (n=20). The number of participants is chosen as per a previous study by Western et al. (12).

Group I (control group): normal room temperature saline irrigation protocol without occlusal reduction

Group II (occlusal reduction group): normal room temperature saline irrigation protocol with occlusal reduction

Group III (cryotherapy group): final irrigation with cold saline (2.5C-4C) without occlusal reduction

7.4. Study settings

Out-patient clinic, MDS Endodontics postgraduate clinics, Thumbay Dental Hospital

7.5. Sample size estimation:

Sixty healthy patients

$$n = \frac{n_0}{1 + \frac{(n_0 - 1)}{N}}$$

7.6. Duration of study

The proposed research will be conducted over a period of 12 months. Details are given in the Gantt chart.

7.7. Study instrument & validation procedure

- Post-endodontic pain will be measured by a visual analog scale (VAS) from 1 to 10.
- The temperature of the cold saline should be 2-4 °C. The saline will be placed in a refrigerator with a thermometer sensor to confirm the 2 to 4°C temperature range.
- After removal, the temperature of the cold saline will be preserved by keeping the irrigation syringes in a special box filled with ice with a thermometer.
- The thermometer will be calibrated according to the manufacturer's instructions.

7.8. Ethical issues

The proposal will be submitted to the Institutional Review Board of Gulf Medical University Ajman, UAE. After obtaining the approval the research will be conducted. The confidentiality, anonymity, and privacy of the members will be kept up with.

The patient will be asked to sign a printed consent form explaining the aim of the study and to fill the pain scale chart postoperatively at 6, 24, 48, 72 hours, and 7 days, after root canal treatment and return it to the operator at day 8.

7.9. Methodology

Sample selection:

The study will be conducted on 60 first mandibular molars; with 20 first mandibular molars in each group (n=20). The patient will be asked to pick an opaque sealed envelope that will contain a number from 1 to 3. The resultant number will determine in which group are the participants to be placed. Double blinding will be maintained in this study as the operator and the patients will not be aware of their group/used irrigant.

Group I (control group): normal room temperature saline irrigation protocol without occlusal reduction

Group II (occlusal reduction group): normal room temperature saline irrigation protocol with occlusal reduction

Group III (cryotherapy group): final irrigation with cold saline (2.5 C°- 4 C°) without occlusal reduction

Procedural steps:

- 1) Vitality will be assessed using cold tests and electric pulp testing before the procedure is carried out. Besides, mobility, palpation, and percussion tests will be done to assess periapical health. In order to ensure that the cold and electrical pulp tests are working, and a response is elicited, both tests will be carried out on patients not included in the study.
- 2) All the patients will receive local anesthesia: 2% lidocaine with 1:100,000 epinephrine.
- 3) Each tooth will be isolated using a rubber dam, and the access cavity will be prepared using a round bur (no.4) and tapered fissure diamond bur (NO173) under copious water.
- 4) After removal of coronal pulp tissues using a sterile excavator, the working length will be determined with stainless steel hand K-files size #10 and the use of an apex locator and confirmed using intraoral periapical radiographs.
- 5) Hand instrumentation till 15 size K file.
- 6) All the canals will be prepared using Protaper Gold rotary files till the file F2 (20/0.06) using the X-Smart Plus endodontic motor.
- 7) Apical patency will be maintained throughout the shaping procedure using the #10 file between each instrument.
- 8) All the canals will be irrigated with 10 mL of 3% NaOCl between each file during the whole preparation procedure.
- 9) After completion of cleaning and shaping in groups I and II, all the canals will be flushed with a final rinse of saline and dried using appropriate size paper points and obturated using the appropriate technique by gutta percha, and permanent composite restoration will be given.
- 10) After completion of cleaning and shaping in group III, 20 ml cryo-treated saline maintained at a temperature of 2°C–4°C will be irrigated for 5 min in each canal.
- 11) All the participants will receive a sheet containing VAS after the procedure. After 6, 24, and 48h, patients are to record the intensity of pain in the area of the root canal (using VAS

from 1 to 10). Analgesic pills that had been taken by the patient are to be recorded on the patient's

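### Sections 7.1 and 7.9 disagree on who is blinded, and the procedures as written do not support blinding of the operator

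*Protocol*

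**What the plan says.** The protocol makes two statements about blinding, each placed directly after the same account of a patient drawing a sealed opaque envelope.

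- Section 7.1 (Research design): "Single blinding will be maintained in this study as patients will not be aware of their group/used irrigant".
- Section 7.9 (Methodology, Sample selection): "Double blinding will be maintained in this study as the operator and the patients will not be aware of their group/used irrigant".

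The arms are set out in sections 7.3 and 7.9:

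- The control arm is given as "Group I (control group): normal room temperature saline irrigation protocol without occlusal reduction".
- The second arm adds grinding to the same rinse and is given as "Group II (occlusal reduction group): normal room temperature saline irrigation protocol with occlusal reduction".
- The third arm, cryotherapy, has a final cold-saline irrigation and its contacts are not reduced.

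Section 6 defines occlusal reduction as a procedure in which "occlusal contacts are highlighted and grinded". Step 10 of section 7.9 gives group III "20 ml cryo-treated saline maintained at a temperature of" 2 to 4 °C, which "will be irrigated for 5 min in each canal". Section 7.7 says the cold is preserved by "keeping the irrigation syringes in a special box filled with ice with a thermometer". Step 9 gives groups I and II a final saline rinse with no stated volume or duration. The SAP does not mention blinding.

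**The concern.** The two sections give different answers on whether the operator is masked. A report that took its wording from 7.9 would claim a property that the described treatment steps do not appear to allow.

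This matters because the outcome is the patient's own pain score on a visual analogue scale. A subjective score can be influenced by what patients know or guess about their treatment, and by how the person treating them behaves. Readers will therefore judge the result partly on the blinding claim. The protocol's alternative hypothesis also expects less pain with cryotherapy, so a reader would want to know who could have been aware of the arm.

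**Working it through.** There is no figure to recompute, so the check compares the passages.

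**1. The two statements.** Section 7.1 masks the patient. Section 7.9 masks the patient and the operator. They agree on the patient and conflict on the operator. Nothing marks either sentence as superseded.

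**2. What distinguishes the arms to the person delivering them.**

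| Group | Contacts ground | Final rinse |
|---|---|---|
| I | No | Room-temperature saline, volume and time not stated |
| II | Yes | Room-temperature saline, volume and time not stated |
| III | No | 20 ml cold saline, 5 min in each canal, syringes kept on ice |

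Grinding identifies group II. The iced syringes and timed cold rinse identify group III. The absence of both identifies group I. Anyone who performs these steps can therefore name the arm.

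**3. Whether masking the irrigant would be enough.** Both blinding sentences refer to the irrigant used. There are three pairwise comparisons:

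- I v II: same irrigant, different grinding.
- I v III: different irrigant, no grinding in either.
- II v III: different irrigant and different grinding.

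The irrigant differs in 2 of the 3 comparisons. In the remaining one, I v II, even perfect concealment of the irrigant would leave the only difference between the arms in view.

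**4. Whether another safeguard is described.** The text available mentions no second operator, sham reduction, coded or matched syringe, or matched rinse time. The opaque envelope conceals the allocation before it is drawn; it does not mask treatment afterwards. Local anaesthesia and rubber dam are used in every patient and are not presented as masking. They would not hide the grinding or the rinse from the person performing them.

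**5. Patients.** Both sections say patients will be unaware of their group, but neither says how. The patient picks the envelope holding the group number, and the text does not say who opens it or whether the number is shown. Consent pages are not in the public document and step 11 of section 7.9 breaks off mid-sentence, so what patients are told cannot be checked.

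**The case against.** The strongest reply is that the operator's knowledge is inferred. The steps in 7.9 are mostly in the passive voice and do not say who gives the final rinse. Occlusal reduction is in none of the numbered steps, so neither the person who does it nor its timing is stated. A second person could have done the arm-specific work. That stands, and it limits what can be said. A reader might infer that the operator was unblinded for all 60 teeth, or that operator blinding was impossible. Both readings assume that one person did everything, which the protocol does not say. For the same reason, no count of steps completed before the arms diverge is safe.

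A reader might also infer that patients were unblinded. The documents do not show this. Patient blinding is stated twice, and a consent form that explains the aim of the study does not disclose an individual's arm. With consent pages and part of step 11 unavailable, the lack of a described method cannot be treated as proof that none existed.

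Two further inferences fail. The chart goes back to the operator at day 8, but by then the scores through day 7 should already have been written, so its return cannot alter them. The silence on how the envelopes yield 20 per group is a separate missing detail and not evidence of imbalance.

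It is also fair to say that a short SAP on statistical methods need not discuss blinding, and that the investigators know what they did. None of this removes the conflict between 7.1 and 7.9 or supplies a mechanism for the stronger claim.

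**Conclusion.** The point holds in a limited form. The contradiction between 7.1 and 7.9 is explicit and needs no assumption. That double blinding is unsupported as written is a sound inference: the arms differ in acts evident to whoever performs them, and no separation of roles is described. It would change only if a separate person delivered the grinding and the final rinse while the operator was kept unaware. Patient blinding is a point to confirm.

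No size can be put on any bias in the pain scores. The documents do not show how many patients, if any, worked out their arm, or how far such knowledge would move a score. The defect lies in a stated property of the design; the documents do not show that the results are biased. It should be corrected because the wrong label would mislead readers about a self-reported outcome and the correction is cheap.

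**What to change.** Delete the double-blind statement in 7.9 and make 7.1 and 7.9 give the same account. Do not report the trial as double-blind unless a separate person delivered the arm-specific steps; if so, say who did what.

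The SAP, dated November 13, 2024, is in the past tense and already states that age was normally distributed. This suggests that the data have been analysed, so the report is the main place to act. It should state from the team's own records:

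- who was masked and by what means;
- whether patients saw the group number;
- who performed the occlusal reduction and the final rinse;
- when the envelope was opened, and by whom.

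The answers should come from what was done, since the documents do not establish them.

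If recruitment is still open, keep the drawn envelope sealed until the steps common to all arms are complete. The protocol passages must first be reconciled on when occlusal reduction takes place.

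For a completed trial the cost is wording only. The downsides are that the trial can no longer be called double-blind on the procedures as written, and that late opening of the envelope, if adopted, adds a short pause during treatment.

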7.11. Details of data storage

The data gathered from this research will be securely stored in Thumbay Dental Hospital. Preoperative data for each patient will be recorded in the predetermined patient's chart, which includes age, sex, and tooth number before the treatment.

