**NCT number: NCT05722704**

**Official title: Effect of Cryotherapy on Post-endodontic Pain**

**ID: IRB/COD/STD/14/May-2022**

**Date: November 13, 2024**

**Statistical Analysis:**

Categorical data were presented as frequency and percentage values and were analyzed using the chi-square test. Numerical data were presented as mean, standard deviation (SD), median, and interquartile range (IQR) values. They were analyzed for normality using Shapiro-Wilk's test. Age data were normally distributed and were analyzed using one-way ANOVA followed by Tukey's post hoc test. Pain score data were non-parametric and were analyzed using Kruskal-Wallis's test followed by Dunn's post hoc test for intergroup comparisons and Friedman's test followed by Nemenyi post hoc test for intragroup comparisons. Correlations were analyzed using Spearman's rank-order correlation coefficient. The significance level was set at  $p<0.05$  within all tests. Statistical analysis was performed with R statistical analysis software version 4.3.2 for Windows\*.

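### Only Group III's final rinse has a written volume and time, so unless the delivered rinses matched, Group III versus Group I tests a cold-rinse regimen and not saline temperature alone

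*Protocol*

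**What the plan says.** The objective in Protocol section 5 reads: "To compare the intensity of post endodontic treatment pain following final rinse using cold saline in comparison to room temperature saline and occlusal reduction". The independent factors in section 6 likewise tell the two saline conditions apart by temperature only.

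Section 7.3 defines the control, Group I, as "normal room temperature saline irrigation protocol without occlusal reduction". Section 7.9 repeats this, and neither place says what the normal protocol consists of.

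The procedural steps in section 7.9 then give:

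- Step 9, Groups I and II: "After completion of cleaning and shaping in groups I and II, all the canals will be flushed with a final rinse of saline". Drying, obturation and restoration follow. No volume, time or flow rate is stated.
- Step 10, Group III: "20 ml cryo-treated saline maintained at a temperature of 2°C–4°C will be irrigated for 5 min in each canal".

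The SAP compares the groups as follows: "Pain score data were non-parametric and were analyzed using Kruskal-Wallis's test followed by Dunn's post hoc test for intergroup comparisons". It does not mention rinse volume or time.

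**The concern.** The objective needs Groups III and I to differ in the temperature of the final saline and in nothing else that could affect pain. As written, one rinse is fixed in volume and time and the other is left open. An operator could follow steps 9 and 10 to the letter and give a brief flush in Group I and 5 min per canal in Group III.

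The two groups would then differ in temperature, rinse time and possibly rinse volume together. The stake is the interpretation of the result. A difference in pain might be reported as an effect of cold when part of it, or an offsetting part, came from a longer or larger rinse.

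**Working it through.** The plan gives no figure to reproduce on this point, so the check sets the written arms side by side and asks what each contrast can identify.

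**Inputs (Protocol 7.3 and 7.9)**

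| | Group I | Group II | Group III |
|---|---|---|---|
| Final saline temperature | room | room | 2-4 °C (step 10) |
| Final rinse volume | not stated | not stated | 20 ml |
| Final rinse time | not stated | not stated | 5 min in each canal |
| Occlusal reduction | no | yes | no |

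Step 8 does give a volume for all canals, 10 mL of 3% NaOCl between files. That is irrigation during preparation, so it does not equalise the final rinse.

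**What III versus I estimates.** Write T for the effect of cold against room-temperature saline at the rinse used in Group III. Write R for the effect, at room temperature, of Group III's volume and time against whatever Group I received. Then

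III − I = T + R.

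- If the delivered rinses matched, R = 0 and the contrast is T, as the objective intends.
- If they differed, R may be positive, negative or zero. There is one observed contrast and two unknowns, so T cannot be recovered.

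**Can another group separate them?** No. Separation needs a room-temperature group rinsed with Group III's volume and time, and no group is specified that way. Group II follows the same open step as Group I.

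**Can the analysis separate them?** No. Kruskal-Wallis with Dunn compares whole groups. Rinse characteristics that go with group membership cannot be disentangled by the test, and more than 20 patients per group would not change that.

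**Other contrasts.** II versus I is less affected, because both follow step 9, although neither rinse is fixed. III versus II compares two strategies that differ by design.

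**Size of the possible gap in rinse time.** With 3-4 canals per mandibular first molar (assumption), Group III's rinse lasts 5 × 3 = 15 min to 5 × 4 = 20 min per tooth. Step 10 can be read as 20 ml per canal, giving 20 × 3 = 60 ml to 20 × 4 = 80 ml per tooth, or as 20 ml in total. Groups I and II have no figure to set against these, so the gap cannot be calculated. The documents give no estimate of how rinse time or volume affects pain.

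**The case against.** The strongest reply is that matching was probably intended and the text is merely brief. The procedural list is abbreviated elsewhere: step 10 does not mention drying, obturation or restoration for Group III, and no visible step describes how occlusal reduction is done. The group labels distinguish the saline arms by temperature. Section 7.9 also says that "the operator and the patients will not be aware of their group/used irrigant", which fits rinses that are alike apart from temperature. This stands as a reason not to claim that the rinses differed. It does not show that they matched, because no passage requires it.

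A second reply is that a usual-irrigation control is legitimate. The hypotheses, rationale and expected outcome treat cryotherapy as a treatment to be set against occlusal reduction or control, and nothing claims to isolate a thermal mechanism. This also stands in part: III versus I is a valid comparison of regimens. But section 5 names cold against room-temperature saline, so a conclusion in those terms needs equal rinses or must be reworded.

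A reader might be tempted to go further in three ways that the documents do not support.

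- **That rinse details were not recorded.** Section 7.11 lists chart data, "which includes age, sex, and tooth number before the treatment", but that list covers preoperative data only and says nothing about what was recorded during treatment. The text of step 11 also breaks off where recording is discussed.
- **That unequal rinses broke the blinding.** A patient treated once has no other arm's rinse to compare with. Operator blinding is doubtful for other reasons, since syringes come from an ice box and the steps are group-specific. That is a separate issue.
- **That error rates or power are distorted by a known amount.** Any such percentage would rest on an invented rinse effect. If the rinses did differ, a significant result would reflect a true difference between regimens and would not be a false positive.

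**Conclusion.** The point holds in conditional form. It is established from the text that Group III's final rinse has a stated volume and time, that the rinse in Groups I and II has neither, and that no visible passage requires them to be equal. It follows that, if the delivered rinses differed, III versus I cannot attribute a pain difference to saline temperature.

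It is not established that Group I had a shorter or smaller rinse, that any rinse effect exists, or which way it would act. A reader might infer that the comparison is invalid or biased towards cryotherapy. The documents do not support this: randomisation and the planned tests remain sound for the regimens as delivered, and only the attribution to cold is limited.

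Severity is minor to moderate. The gap touches a contrast named in the objective, but the remedy is reporting and wording. The only numerical assumption is 3-4 canals per tooth, used for chair time and volume.

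**What to change.** The SAP is dated November 2024 and is written in the past tense with data properties already described, so treatment appears complete. In that case:

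- Report the final-rinse volume and time delivered per canal in each group, and say whether the figures were recorded at the time or recalled. For Group III, state whether 20 ml was per canal or per tooth.
- Unless the rinses matched, word the III versus I conclusion as the effect of the cold-rinse regimen (20 ml, 5 min per canal) and not of temperature alone.

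This needs no extra patients and no new analysis. The price is a narrower statement about mechanism.

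If any treatment remains, amend step 9 so that Groups I and II receive room-temperature saline at the same volume and time per canal as Group III. The cost is about 15-20 min of extra chair time per tooth (3-4 canals assumed). The upper limit, if all 40 patients in Groups I and II were still untreated, is 40 × 15 = 600 min to 40 × 20 = 800 min, or 10 to 13.3 hours. The amended control would also no longer be usual irrigation, so III versus I would no longer estimate the benefit over normal practice.
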